Radiographs will be taken and collected in the AP pelvis, AP femur and lateral views for the preoperative, 6-week, 1, 2, 3, 4 and 5-year intervals. Additional radiographs will be obtained at the 7-year and 10-year time points at investigational sites that choose to bring their subjects back in for these optional visits.

The AP pelvis and AP femur views allow for observations of any conditions involving the sacral wings, iliac bones, ischium, pubis as well as the femoral head and neck. These views additionally display the critical relationship between the femoral neck's longitudinal axis and the femoral shaft's longitudinal axis for identification of displacement in the event of a femoral neck fracture. The lateral view allows for evaluation of the entire hip joint as well as specifically the femoral head, neck and proximal shaft.⁸ Suggested radiographic technique for the views required is included in Appendix A.

Radiographs will be evaluated by an independent reviewer throughout the course of the study. Radiographic analysis of the femoral component will employ seven zones (Zone 1 - Zone 7) in the AP views and seven zones (Zone 8 – Zone 14) in the lateral view; analysis of the acetabular component will employ three zones (Zone 1 – Zone 3) in the AP views.^{9,10} Numerous parameters will be reviewed by zone, including radiolucency, hypertrophy, and condensation. Radiolucency in at least 50% of a zone and measuring at least 1 mm in width is defined as radiolucency present.

Subsidence, migration and fixation will also be assessed. Subsidence is defined as settling of the prosthetic component in bone, and is related to the distance between fixed bony landmarks and the prosthesis.

CONFIDENTIAL

Biomechanical Measurements:

Preoperatively, study radiographs will be taken by each investigator. From these radiographs, each investigator will determine natural measurements and provide a detailed picture of each patient's level of deformity, as follows.

- Leg length discrepancy (centimeters)
 - Measurement of leg length discrepancy should be determined from the AP pelvis radiograph by drawing lines across both pelvic teardrops to meet both femurs. These lines are to be used as the main reference lines for measuring the distance to the top of each lesser trochanter.¹¹ The difference between these distances is the value of leg length discrepancy.
- Natural femoral offset (millimeters)

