 - Femoral offset should be determined by measuring the perpendicular distance from the center of the femoral head to the axis along the length of the femur.¹²
- Natural femoral neck angle (degrees)
 - Femoral neck angle is the angle between the long axes of the femoral neck and femoral shaft.¹³
- Qualitative assessment of natural femoral version (Retroverted, Neutral, Anteverted)
 - Proximal femoral version reflects the relationship of the axis of the femoral neck to the transcondylar axis of the distal femur.¹⁴ Qualitative determination of whether natural femoral version is retroverted, anteverted or in a state of neutral version should be made from the lateral radiograph.

The investigator at each center will create a preoperative biomechanical measurement plan for each case from templating, reflecting desired postoperative measurements and the component sizes, angles and offsets that will be used to achieve these measurements. All component sizes should be corrected for magnification (if any) prior to data collection on the study Case Report Form (CRF). This may be accomplished by utilizing an external radiographic marker of known dimension prior to taking the preoperative radiograph.¹⁵

CONFIDENTIAL

Preoperative Distance from Planned Center of Rotation

- Vertical distance from the anatomic hip center to the planned center of rotation of the hip (millimeters)
- Horizontal distance from the anatomic hip center to the planned center of rotation of the hip (millimeters)

Components to be Used

- Acetabular cup size
- Femoral neck angle [127°, 132°, 130° (16° version option only)]
- Femoral neck length (millimeters)
- Femoral head size
- Femoral head offset
- Femoral stem size*
- Femoral version (0°, ±8°, ±16°)

*The Rejuvenate® Modular Stem will be available in sizes 7, 8, 9, 10, 11 and 12. The Rejuvenate® Monolithic Stem will be available in sizes 4, 5 and 6; however, **the Rejuvenate® Monolithic Stem may not be used according to this protocol.** Patients requiring a femoral stem in size 4, 5 or 6 should not be enrolled into the study. Investigators should template the femoral stem size to be used prior to completing the Inclusion/Exclusion CRF for enrollment into the study.

Additional Planned Measurements

- Amount of leg length to be restored (centimeters)

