 - Measurement of leg length discrepancy should be determined from the AP pelvis radiograph by drawing lines across both pelvic teardrops to meet both femurs. These lines are to be used as the main reference lines for then measuring the distance to the top of each lesser trochanters.¹⁶ The difference between these distances is the value of leg length discrepancy. From this value, the investigator will determine the amount of leg length he/she plans to restore.
- Femoral offset to be achieved (millimeters)
- Qualitative assessment of postoperative planned femoral version (Retroverted, Neutral, Anteverted)

A postoperative check of biomechanical measurements will be performed by the investigator at each site from the 6-week radiographs to confirm the degree to which the

CONFIDENTIAL

preoperative plan was achieved. If an AE for instability exists, the postoperative check will be taken again at applicable postoperative intervals to confirm whether or not changes have occurred.

Postoperative Distance from Planned Center of Rotation

- Vertical distance from the postoperative hip center to the planned preoperative center of rotation of the hip (millimeters)
- Horizontal distance from the postoperative hip center to the planned preoperative center of rotation of the hip (millimeters)

Additional Postoperative Measurements

- Leg length discrepancy (centimeters)
- Final femoral offset (millimeters)
- Final femoral neck angle used [127°, 132°, 130° (16° version option only)]
- Qualitative assessment of replaced femoral version (Retroverted, Neutral, Anteverted)

These postoperative values will be compared to the preoperative plan to evaluate the degree of patient matching achieved with the Rejuvenate® Modular Hip System.

Component sizes used intraoperatively will be automatically determined from catalog numbers provided on the Surgical Details CRF.

Biomechanical measurements are outlined in Appendix B.

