9.1.2 Secondary Efficacy Parameters

The secondary efficacy parameters include:

- Biomechanical measurement change from preoperative plan at 6-week visit
- HHS at each visit
- SF-12 scores at each visit
- LEAS at each visit

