9.1.5 Secondary Efficacy Analysis

A two-sided 0.05 alpha level will be used.

For comparison of biomechanical measurements between a preoperative plan and postoperative measurements within the Rejuvenate[®] Modular Hip System group, a t-test or Wilcoxon test will be used.

Independent group t-tests will compare HHS, SF-12 and LEAS at each time point between the Rejuvenate[®] Modular Hip System and Secur-Fit[™] HA monolithic femoral stem groups. In addition, a paired t-test will compare the results preoperatively with each postoperative evaluation within the Rejuvenate[®] Modular Hip System group.

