L. FEMORAL HEAD SIZE:	  mm
M. FEMORAL NECK ANGLE: (Check one)	 127°  130°  132°
N. FEMORAL NECK LENGTH (mm): (Check one)	 30  34  38  42
O. FEMORAL STEM SIZE (mm): (Check one)	 7  8  9  10  11  12
P. FEMORAL VERSION: (Check one)	 -16°  -8°  0°  +8°  +16°

*The Rejuvenate® Modular Stem will be available in sizes 7, 8, 9, 10, 11 and 12. The Rejuvenate® Monolithic Stem will be available in sizes 4, 5 and 6; however, **the Rejuvenate® Monolithic Stem may not be used according to this protocol**. Patients requiring a femoral stem in size 4, 5 or 6 should not be enrolled into the study. Investigators should template the femoral stem size to be used prior to completing the Inclusion/Exclusion CRF for enrollment into the study.

Additional Planned Measurements

- **Amount of leg length to restore** (centimeters)
- **Femoral offset to achieve** (millimeters)
- **Qualitative assessment of planned postoperative femoral version** (Retroverted, Neutral, Anteverted)

F. LEG LENGTH TO RESTORE:   cm	G. FEMORAL OFFSET TO ACHIEVE:    mm
H. PLANNED POSTOPERATIVE FEMORAL VERSION: (Check one)  Retroverted  Neutral  Anteverted	

Postoperative Measurements

A postoperative check of biomechanical measurements will be performed by the investigator at each site from the 6-week radiographs to confirm the degree to which the preoperative plan was achieved.

If an AE for instability exists, Stryker will work with an independent radiographic reviewer to re-evaluate the case and confirm whether or not the postoperative biomechanical measurements have changed as a result of the AE. If changes have occurred, the reviewer will continue to assess radiographs at each applicable postoperative interval until the hip has stabilized.

Postoperative Distance from Planned Center of Rotation

- Vertical distance from the postoperative hip center to the planned preoperative center of rotation of the hip (millimeters)

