D D M M M Y Y Y YOPERATIVE SIDE: Right Left
(use one form per side)VISIT:
 6 Week Unscheduled-
 Reviewer Collected**I. ACTUAL POSTOPERATIVE MEASUREMENTS****A. LEG LENGTH DISCREPANCY:**

Yes*
 No

* If Yes, indicate longer side:

Operative
 Contralateral

B. FINAL FEMORAL OFFSET: mm**C. QUALITATIVE ASSESSMENT OF REPLACED FEMORAL VERSION:**

Use the Lateral Radiograph:

Replaced femoral version: (Check one)

Retroverted
 Neutral
 Anteverted

D. POSTOPERATIVE DISTANCE FROM PLANNED CENTER OF ROTATION:

Vertical distance from the postoperative hip center to the planned preoperative center of rotation of the hip:

 mm

Horizontal distance from the postoperative hip center to the planned preoperative center of rotation of the hip:

 mm**II. COMMENTS**

--

INVESTIGATOR / REVIEWER
NAME (PRINT):INVESTIGATOR / REVIEWER
SIGNATURE:DATE: / / / / /
D D M M M Y Y Y Y

Stamp Date Received:

INITIAL/DATE:
Receipt _____

Entry _____

Verification _____
Monitored _____

For Stryker Use Only

Keep this reminder sheet in the subject's study binder.
Please do not send to Stryker.

Stryker®

REJUVENATE® MODULAR HIP SYSTEM
X-RAY REMINDER SHEET

[name]

Instructions for Stryker Orthopaedics Clinical Study X-ray Labels

1. Based on the protocol's radiographic evaluation schedule, obtain copies of the subject's X-rays.
 - a. If the subject is bilateral and the view includes both sides, **two** copies of the films are needed.
 - b. For viewing purposes, the film should always be the mirror image (not inverted).
 - i. If the subject's operative side is (R), the joint should be on the (L) side of the film when being viewed.
 - c. **Markers** for (R) and (L) should be on the correct side.
 - i. If incorrect or missing, the film should be marked correctly.
2. **Complete a white X-ray label** to ensure accurate identification of each film.
(similar to CRF header information)
 - a. Subject ID
 - b. Subject Initials
 - c. Date of X-ray
 - d. Visit Interval
 - e. Operative Side
 - f. View
3. **For films**, affix the label to the bottom of the film:
 - a. Should not obscure the view
 - b. Should not obscure the implant
 - c. Should not cover the subject imprint details
 - d. Should be positioned horizontally according to the view
4. **For digital X-rays**, attach completed unpeeled labels to the CD case and write the Subject ID on the CD.

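### As read from the PDF, item A on both biomechanical CRFs records leg length discrepancy only as Yes/No and longer side, so the radiographic leg-length comparison with the plan cannot be computed from those forms

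*Combined protocol and SAP*

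**What the plan says.** Section 2.1.2 and Appendix B describe a radiographic measurement. Reference lines are drawn across the pelvic teardrops on the AP pelvis film, and the distance to each lesser trochanter is measured. "The difference between these distances is the value of leg length discrepancy". Both places list the discrepancy in centimeters, preoperatively and at 6 weeks. Sections 7.1 and 7.3 list the same item in millimeters.

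The plan side is a number: the preoperative biomechanical form has "F. LEG LENGTH TO RESTORE" with a cm entry. Section 2.1.2 then states the purpose: "These postoperative values will be compared to the preoperative plan to evaluate the degree of patient matching achieved". Section 9.1.2 makes this a secondary efficacy parameter, "Biomechanical measurement change from preoperative plan at 6-week visit", and for that comparison 9.1.5 says "a t-test or Wilcoxon test will be used".

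In Appendix F, item A of the preoperative and of the postoperative biomechanical CRF consists of Yes or No, then "If Yes, indicate longer side" with the choices operative and contralateral. The excerpts in Appendix B show the same layout. Section 11.4 makes the CRFs the main instrument for data collection.

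**The concern.** The text defines a continuous quantity and plans a test that needs one, but the form made for it captures a category. Leg length is one of the three anatomical targets that section 1.2 names for the device (with offset and version), and 1.2 says this study will supply the supporting data. If sites fill in the forms as they read, the analyst has an intended correction in cm and no radiographic amount, before or after surgery, to set against it.

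The follow-up of instability events has the same gap. Section 2.1.2 and Appendix B call for repeat measurement after such an event, and the reviewer-collected visit uses the same postoperative form. A change in discrepancy that alters neither its presence nor its side would leave no trace there.

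**Working it through.** The plan gives no figure to reproduce. The check traces leg length from requirement to form, then asks whether the tested difference can be recovered.

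**1. Requirement against field**

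| Quantity | Required | Field on the biomechanical CRF |
|---|---|---|
| Preoperative discrepancy | Amount (cm in 2.1.2 and Appendix B; mm in 7.1) | Yes/No, longer side |
| Leg length to restore | Amount (cm in 2.1.2 and Appendix B; mm in 7.1) | Number, cm |
| 6-week discrepancy | Amount (cm in 2.1.2 and Appendix B; mm in 7.3) | Yes/No, longer side |
| 6-week femoral offset | mm | Number, mm |
| 6-week hip centre, vertical and horizontal | mm | Number, mm (two fields) |

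Of the four lengths to be measured at 6 weeks (discrepancy, offset, two centre distances), three have a numeric field and one does not.

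**2. Can the difference be recovered?**
Let D0 and D6 be the signed discrepancies before surgery and at 6 weeks (operative side longer = positive), and R the length to restore, taken here as lengthening of the operative leg.

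Planned residual = D0 + R. Deviation from plan = D6 − (D0 + R).

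The forms supply R but only the signs of D0 and D6. Two hips with assumed values, contralateral leg longer throughout:

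- Hip 1: D0 = −3.0 cm, R = 2.0 cm, planned residual = −3.0 + 2.0 = −1.0 cm. D6 = −0.3 cm. Deviation = −0.3 − (−1.0) = +0.7 cm.
- Hip 2: D0 = −2.0 cm, R = 2.0 cm, planned residual = −2.0 + 2.0 = 0.0 cm. D6 = −1.5 cm. Deviation = −1.5 − 0.0 = −1.5 cm.

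Both hips produce the same entries: Yes, contralateral; 2.0 cm; Yes, contralateral. One ended 0.7 cm longer than planned and the other 1.5 cm shorter, and these forms cannot tell them apart. Assuming full restoration in every case would fix the planned residual at zero, but 2.1.2 leaves the amount to the investigator, and D6 would still be unknown for every hip marked Yes.

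**3. Is it a conversion artefact?**
On the two Appendix F forms, every other free numeric measurement keeps its unit:

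- Preoperative, 8 fields: offset, neck angle, two centre distances, length to restore, offset to achieve, cup size, head size.
- Postoperative, 3 fields: final offset, two centre distances.

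That is 8 + 3 = 11 of 11. Leg length discrepancy shows a unit in 0 of 4 renderings (two in Appendix F, two in Appendix B).

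**4. Other sources of a number**
- The Functional Evaluation forms, preoperative and 6-week, have a deformity item at 3.2 cm with a cm entry to specify.
- The Surgical Details form has change in leg length in mm, but only where navigation was used, and as an intraoperative value.
- AP pelvis films are collected at both time points.

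**The case against.** Three counter-arguments have force.

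**Conversion loss is not excluded.** The neck-angle degree sign is missing from the Appendix B excerpt but present on the Appendix F form, so a unit did drop out on a copy of this very page. Number boxes often leave no trace in the text, so only the missing unit is evidence. The Appendix B excerpts appear to reproduce the Appendix F forms, so the four renderings are really two layouts. This stands, and it is why the printed forms come first.

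**A number exists elsewhere.** The Functional Evaluation entry is in cm at both time points, and the longer-side box for the same visit can give it a sign. Appendix B also tells sites to make source documents reflect these measurements, and the films can be re-measured. A reader might infer from item A that no leg-length amount is collected anywhere, or that the study could not tell a hip left 1 mm long from one left 20 mm long. The documents do not support that: it is true of the biomechanical forms alone. What remains is that the Functional Evaluation entry is not said to be radiographic or to use the teardrop method, and nothing assigns it to the 9.1.5 comparison.

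**The forms are drafts.** Section 11.1 says so, and 11.4 refers to a separate completion guide that is not among the documents. That guide might ask for an amount, but item A as it reads gives no place to enter one.

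**Conclusion.** The point holds within these limits. As the text reads, the radiographic leg-length component of the plan-versus-6-week comparison cannot be computed from the biomechanical CRFs, for any of the 240 planned hips. Both sides are affected: without the preoperative amount the planned residual is undefined, and without the 6-week amount there is no result to compare with it. A tabulation of presence and side remains possible.

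It would go too far to say that the biomechanical analysis as a whole fails. Offset and the two centre distances have numeric fields, and 9.1.5 can be run on them. The primary endpoint is untouched. This is one component of one within-group secondary endpoint, worth correcting because the correction is nearly free.

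The conclusion assumes that item A has no number box on the printed forms. The agreement of the renderings and the surviving units on the other Appendix F fields make that likely, but they do not prove it.

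**What to change.** 1. Look at the printed preoperative and postoperative biomechanical CRFs. If item A already has a numeric box, only the unit and the analysis wording below need attention.
2. If it has none, add a numeric field to item A on both forms. Take the sign from the longer-side box (operative longer positive, contralateral longer negative) and enter 0 when there is no discrepancy.
3. Fix one unit and use it throughout, reconciling the centimeters of 2.1.2 and Appendix B with the millimeters of 7.1 and 7.3, for both the discrepancy and the length to restore.
4. In 9.1.5, state that the 6-week signed discrepancy is compared with the planned residual, that is, the signed preoperative discrepancy combined with the length to restore, and state the direction convention for the latter.
5. State whether the Functional Evaluation leg-length entry has any role in this analysis.

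The cost is one field on two forms the protocol still calls draft, plus a few sentences of text. The investigator already makes the measurement under Appendix B, so no visit, film or procedure is added. If forms have already been completed without the amount, it would have to come from source records or from re-measuring the collected films.

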Such events will not be captured on the AE CRF but rather will be captured on the postoperative functional evaluation at the 6-week, 1-year, 2-year, 3-year, 4-year and 5-year time points (as well as at optional 7 and 10-year visits). On these functional evaluations, investigators and SCs will be prompted to question subjects as to whether they have seen a doctor for any reason, been hospitalized for any reason or have a current impediment to their function.

The following decision tree facilitates identification of AEs for which reporting is required under this study protocol:

CONFIDENTIAL

Figure 1
Adverse Event Decision Tree

CONFIDENTIAL

General Physical Examination Findings

At screening for inclusion into the study, any clinically significant abnormality should be recorded as a preexisting condition and reported on the Demographics CRF. From the time of consent forward, any new clinically significant findings or abnormalities that meet the definition of a protocol defined AE must also be recorded and documented as an AE.

Adverse Event Reporting Period

The study period during which AEs must be reported is normally defined as the period from the initiation of any study procedures to the end of the study treatment follow-up. The start of study procedures is considered to be the point of consent. Any AEs which fit the protocol defined reportable events must be reported from the time of consent until study completion.

At each contact with the subject the investigator must seek information on AEs by specific questioning and, as appropriate, by examination. Information on protocol defined AEs should be recorded immediately in the source document and also in the appropriate AE module of the CRF. All clearly related signs, symptoms and abnormal diagnostic procedure results should be recorded in the source document and grouped under one diagnosis as appropriate. The clinical course of each event should be followed until resolution or until it is determined at the end of the study that the AE will not resolve.

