8.2 General Adverse Event Definitions

Following is a list of general AE definitions. For the purposes of this study, only SAEs, excluding elective procedures, as well as all AEs related to the operative site should be reported.

Adverse Event

An **AE** is any untoward medical occurrence in a clinical investigation subject, which changes the medical baseline of the subject. An AE can be an unfavorable and unintended sign, symptom or disease, whether or not related to the study device (AEs may also be referred to as complications). See Section 8.1, Reporting of Adverse Events, for the AE reporting requirements for this study.

CONFIDENTIAL

Anticipated Adverse Event

An **anticipated AE** is an AE, of which the nature, severity or degree of incidence is known and identified in applicable product labeling, published literature or study protocol. The list of anticipated events is provided in Section 12, Risk/Benefit Assessment.

Serious Adverse Event

A **SAE** meets one or more of the following definitions:

- Resulted in in-patient hospitalization
- Resulted in prolonged existing hospitalization
- Resulted in persistent or significant disability/incapacity
- Resulted in permanent impairment of a body function or permanent damage to a body structure
- Necessitated medical or surgical intervention to preclude permanent impairment of a body function or permanent damage to a body structure
- Was a life-threatening situation
- Resulted in patient death

Elective procedures meeting the definition of an SAE do not need to be reported as AEs according to this study protocol.

Adverse Device Effect

An **adverse device effect** (ADE) is a negative change in the subject's health that may have been caused by, or associated with, the use of the device.

Unanticipated Adverse Device Effect

An **unanticipated adverse device effect** (UADE) is any serious adverse effect on health, safety or any life-threatening problem or death caused by, or associated with, a device if that effect is a problem or death not previously identified in nature, severity or degree of incidence, or any other unanticipated serious problem associated with a device and related to the rights, safety or welfare of subjects.

CONFIDENTIAL

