- Normally without using a rail
- Normally using a railing
- In any manner
- Unable to use stairs

F. SOCKS / SHOES (Check One)

- With ease
- With difficulty
- Unable

G. SITTING (Check One)

- Any chair, 1 hour
- High chair, 1/2 hour
- Unable to sit comfortably in any chair

H. PUBLIC TRANSPORTATION

- Able to use
- Not able to use

I. ABSENCE OF DEFORMITY (Operative side only)

Yes No

Yes No

Fixed flexion contracture < 30°

Fixed internal rotation in extension < 10°

Fixed adduction < 10°

Leg length discrepancy < 3.2 cm

 (Specify) . cm**K. RANGE OF MOTION** (Operative side only)

Permanent (Fixed) Flexion

 °

Adduction to

 °

Flexion to

 °

External Rotation in Extension to

 °

Abduction to

 °

Internal Rotation in Extension to

 °**J. THIGH PAIN** (Operative side only)Present at current visit: Yes* No

*If Yes, complete the following:

Describe History or Causative Event:

Is the Thigh Pain Distal?

 Yes No

Is the Thigh Pain Activity Limiting?

 Yes No

Is the Thigh Pain Constant?

 Yes No

What is the subject's perception of the Thigh Pain level on a One to Ten (1-10) scale?: (Check One)

Very slight pain Worst Pain
1 2 3 4 5 6 7 8 9 10

[name]

SUBJECT ID: **6 8**
Study # Site # Subject #**GENERAL INFORMATION**SUBJECT INITIALS:
(If there is no middle initial please use "-") VISIT: 6 Week 1 Year 2 Year 3 Year 4 Year 5 Year 7 Year 10 Year**IV. EVENTS**L. Have there been any protocol defined Adverse Events since the last visit? Yes* No

*If Yes, complete an AE form for each.

USE THIS SECTION TO REPORT MEDICAL EVENTS OTHER THAN PROTOCOL DEFINED ADVERSE EVENTS.M. Has the subject seen a doctor for any medical event since the last visit? Yes* No

*If Yes, specify:

N. Has the subject been hospitalized for any elective surgery since the last visit? Yes* No

*If Yes, specify and check all that apply:

 Contralateral Hip Contralateral Knee Ipsilateral Knee Contralateral Shoulder
 Ipsilateral Shoulder Cataract Other (Specify)

*Provide details:

O. Is anything currently affecting the subject's function? Yes* No

*If Yes, specify:

V. COMMENTS

INVESTIGATOR NAME (PRINT):

INVESTIGATOR SIGNATURE:

DATE: / /
 D D M M M Y Y Y YINITIAL/DATE:
Stamp Date Received:
Receipt
Entry
Verification
Monitored
For Stryker Use Only

[name]

SUBJECT ID: **6 8**
Study # Site # Subject #**GENERAL INFORMATION**SUBJECT INITIALS:
(If there is no middle initial please use "-") VISIT DATE: / / / / / / /

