5. Send the labeled X-rays to **Data Entry** for processing. (Data Entry affixes a color-coded visit interval label over the subject imprint to obscure the subject's personal health information.)
6. When the X-ray label supply is low, please contact the Clinical Study Manager to request more labels.

SUBJECT ID:	6 8						VISIT:	 Pre-op	 6 Week	 1 Year	 2 Year	 3 Year	 4 Year	 5 Year	 7 Year	 10 Year
Study #	Site #	Subject #				Obtained	Not Obtained (Complete and submit one Protocol Deviation Form per interval)						N/A			
1. A/P Pelvis																
2. A/P Femur																
3. Lateral																
COMMENTS																
<hr/> <hr/>																
Date X-rays Sent: _____							Tracking Number: _____									

14Apr2010

Keep this reminder sheet in the subject's study binder.
Do not send to Stryker.

[name]

SUBJECT ID: **6 8**
 Study # Site # Subject #**GENERAL INFORMATION**SUBJECT INITIALS:
(If there is no middle initial please use "-") QUESTIONNAIRE
COMPLETED BY: Visit Mail PhoneOPERATIVE SIDE: Right Left
(Use one form per side)VISIT: 6 Year 7 Year 8 Year 9 Year 10 Year**I. HIP QUESTIONS**1. Do you have any pain in your hip that has the study hip replacement? YES* NO

Subject comment: _____

2. Are you satisfied with the results of your study total hip replacement? YES NO*

Subject comment: _____

3. Have you had any surgery on your study hip during the time since your last study required visit/contact?

 YES* NO

Subject comment: _____

Subject, please initial and date here: _____

DATE: / /
 D D M M M Y Y Y Y**II. FOR COORDINATOR'S USE ONLY**Please specify below for responses marked with an asterisk.

A. *Coordinator, if Yes in Question 1 above, specify, complete Adverse Event form and provide date:

AE Onset Date: / /
 D D M M M Y Y Y Y

B. *Coordinator, if No in Question 2 above, specify:

C. *Coordinator, if Yes in Question 3 above, specify, complete Adverse Event form and provide date:

AE Onset Date: / /
 D D M M M Y Y Y Y

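### The year 6–10 questionnaire requires an AE form for any study-hip pain without the section 8.2 change test, and has no prompt for SAEs or resolved non-surgical hip events

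*Combined protocol and SAP*

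**What the plan says.** The Follow-up Questionnaire in Appendix F is used at years 6, 7, 8, 9 and 10. It has three patient questions:

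- Question 1: "Do you have any pain in your hip that has the study hip replacement". A Yes leads to the coordinator instruction "Coordinator, if Yes in Question 1 above, specify, complete Adverse Event form and provide date", followed by a field for the AE onset date.
- Question 2 asks about satisfaction. A No leads only to "Coordinator, if No in Question 2 above, specify", with no AE form.
- Question 3: "Have you had any surgery on your study hip during the time since your last study required visit/contact". A Yes leads to an AE form.

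Section 7.4 lists satisfaction, pain and study-hip surgery as the minimum content. It allows completion by telephone, at home or in clinic, and the form itself has a tick box for mail. Sections 3.4 and 7.4 leave the in-office visits at years 7 and 10 to the choice of the site.

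Section 8 sets the AE rules. Section 8.2 requires an AE to be an occurrence "which changes the medical baseline of the subject", and says that a symptom can qualify. Section 8.1 makes two classes reportable: serious events other than elective procedures, and operative-site events of any seriousness. On the period it states: "Any AEs which fit the protocol defined reportable events must be reported from the time of consent until study completion". On solicitation it states: "At each contact with the subject the investigator must seek information on AEs by specific questioning". Section 8.4 adds that events between visits must be recorded.

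The postoperative Functional Evaluation form, required up to year 5, handles this differently. Its pain and thigh-pain items carry no AE instruction, and item L asks separately: "Have there been any protocol defined Adverse Events since the last visit".

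**The concern.** Two features of the form do not line up with section 8.

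First, the pain rule has no threshold. Any current pain calls for an AE form, whether it began last month or has been stable for years. Section 8.2 asks for a change from the subject's baseline. Up to year 5 a pain score does not by itself call for an AE form; from year 6 a pain answer does.

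Second, the one instrument that every subject must complete in years 6–10 does not ask the general AE question. A hospitalisation, or a hip event treated without surgery and since resolved, can go unmentioned by a subject who answers all three questions correctly.

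Section 9.2.2 plans AE listings, numbers and percentages of cases or subjects, 95% confidence intervals and, if appropriate, a Fisher's exact test against the Secur-Fit HA group. For follow-up after year 5 those rates would depend partly on how this form is worded. The documents do not say how late events were solicited in the historical control, so like-for-like ascertainment cannot be assumed.

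**Working it through.** The plan states no figure for late AE capture, so there is nothing to reproduce and no formula to apply. The check sets the form beside the rules.

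**Step 1: which contacts are required.** The Evaluation Schedule and section 3.4 require five questionnaires, at years 6 to 10. The Functional Evaluation, which carries item L, is optional at years 7 and 10 and absent at years 6, 8 and 9. At a site that does not opt in, the questionnaire is the only required contact for five years.

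**Step 2: what each kind of event does on the form.**

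| Event in years 6–10 | Status under 8.1 and 8.2 | What the questionnaire does |
|---|---|---|
| New or worse study-hip pain, present at completion | Fits: a symptom, at the operative site | AE form through Question 1; agrees |
| Study-hip pain unchanged since the last contact | Does not clearly meet the change test as a new event | AE form still required; mismatch |
| Surgery on the study hip | Reportable unless elective | AE form through Question 3; agrees |
| Non-surgical hip event, still painful | Reportable | Reached indirectly through Question 1 |
| Non-surgical hip event, resolved and painless | Reportable | No prompt; gap |
| Non-elective hospitalisation for another cause | Reportable as an SAE | No prompt; gap |
| Death | Reportable | Handled elsewhere: the Study Termination form calls for an AE form |

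**Step 3: whether the mode of completion closes the gap.** In a telephone interview or clinic visit, staff can add the questioning that section 8.1 requires. When the form is completed at home and mailed, only its printed questions reach the subject, and none of them is a general AE question. That route does not carry out the section 8.1 duty.

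**Step 4: which analyses are touched.** The primary comparison in section 9.1.4 is stem/neck revision or removal at 5 years, before the questionnaire is first used. Late survivorship is still served by Question 3. What remains exposed is the AE reporting of section 9.2.2 for events after year 5.

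**The case against.** The strongest reply is that the form does not replace section 8. The duty to question at each contact, the recording of between-visit events and the reporting period to study completion all still apply. Section 7.4 calls the content a minimum, every question has a comment line, and item L is asked wherever the optional visits are held. All of this stands. It makes the second half a gap in solicitation. A reader might infer that the form contradicts the AE definition in both directions; the documents do not support that. Leaving out a question does not contradict a definition, and for pain the mismatch is confined to unchanged symptoms, because new or worse operative-site pain is a proper AE.

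A reader might also infer that the same pain must generate a fresh AE each year. That does not follow. The form asks for the onset date of the event, not the questionnaire date, and the AE CRF allows an event to be left unresolved and updated later, so continuing pain can be carried as one open event. Nor is it established that such pain would not have been an AE at year 5, since item L was asked then.

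Multiplying an assumed pain rate by hips and questionnaires to predict a number of AE forms is also unsupported. The documents give no pain rate. Section 9.2.2 summarises cases or subjects, so repeat forms in one hip add no cases, and form counts cannot be set against the case percentages in Table 4.

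The doctor-visit question next to item L should not be read as a second AE prompt. Its section is headed as being for events other than protocol-defined AEs.

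A low threshold for pain can be defended as sensitive once clinic visits are optional, and a filter based on patient recall could lose an early signal. That is a good reason to keep recording every pain answer. It is not a reason to classify every one as a new AE.

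Finally, the decision tree (Figure 1), the first part of the AE CRF and the separate CRF guide mentioned in section 11.4 are not visible here. Any of them might hold a baseline-change rule.

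**Conclusion.** The point holds in a limited form. As drafted, the questionnaire requires an AE form for any current study-hip pain without the section 8.2 change test. It also has no prompt for SAEs, hospitalisation or resolved non-surgical hip events, all within a period when section 8.1 still requires reporting and active questioning. A mailed form leaves that questioning undone.

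The reach is five required questionnaires per subject, in a study of 240 enrolled cases, and the AE rates for years 6–10. The size of any error in those rates cannot be calculated, because the documents give neither a late pain rate nor a late event rate. The 5-year primary endpoint and the late revision question are not affected.

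The conclusion assumes that no unseen instruction supplies the missing test or prompt. It is a worthwhile, low-cost reconciliation of a draft form with the protocol's own AE rules. It is not a flaw in the main analysis.

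**What to change.** Revise the draft questionnaire before it is first used at year 6, and reconcile it with section 8.

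1. Add one lay question based on item L, and add it to the minimum content in section 7.4. For example: Since your last study contact, have you been in hospital for any reason, or had a dislocation, infection, fracture, blood clot or doctor visit for your study hip? A Yes is assessed by the coordinator against section 8.1, where elective procedures drop out.
2. Keep recording every answer to Question 1. Change the coordinator instruction so that a Yes is first checked against section 8.2, that is, whether the pain is new or worse than at the last contact. Open a new AE only if it is, and update the existing AE form if one is already open.
3. Check that the decision tree, the full AE CRF and the CRF guide give the same rule.

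The cost is a revision of one CRF and of section 7.4, a patient form one question longer, and a few more call-backs by coordinators. No visits are added.
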